6.1 Data Collection and Management

Data collected at each time point (T1) - (T4) will be extracted from participants rehabilitation centre files with names replaced by individual participants study identification number to organise and collect the data. This data will be stored, in a locked filing cabinet at the study site in paper form.

After the intervention the consenting participants' paper data will be collected by the associate research investigator and converted to electronic files. These electronic files will be uploaded to Excel in a password protected file for storing and analysis. The database housing this information will be stored on a secure Macquarie University server and Cloudstor and will be password protected. Only the named research team will have access to the files. Any paper data will be de-identified and stored in a secured archive onsite at Macquarie University for a period of 7 years post study completion. The electronic data files will be kept on the secure Macquarie University server and Cloudstor indefinitely.

6.2 Data Analysis

De-identified data analysis will be conducted using SPSS Version 25. Demographic data will be

reported via descriptive statistics. Adherence data will be calculated from each week and from week 0 (T1) to week 3 (T2) and will be reported as mean repetitions per hour, session, and week and then as a percentage of overall sessions attended. Acceptability and self-management data will be taken from the surveys and will be reported as frequencies comparing time points week 3 (T3) and week 6 (T4). Acceptability data from the practice sheets use will be calculated from each week and from week 0 (T1) to week 3 (T3) and will be reported as mean values per week and then as a percentage overall. Paired t-tests will be used to analyse within group change over time for the clinical outcomes between week 0 (T1) to week 3 (T3) and between week 0 (T1) to week 6 (T4). Differences will be reported as a mean and 95% confidence interval.

7 Research Outcomes and Future Plans

Participants will have the opportunity to review their initial (T1) and post intervention (T3, T4) results with their treating allied health clinician (as per usual care at the study site). A publication and conference presentation are expected from this project to satisfy the requirement of the Master by Research candidature. Participants who have consented to participation in the research will be informed that only de-identified group data will be presented.

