either at home or in the clinic and if needed an allied health clinician or carer will be available to
support filling out the survey and collecting the surveys from participant. Completed surveys will be
filed in the participant's rehabilitation centre file and in a participant's paper workbook. Participants
will be followed up in three weeks (T4) by the same allied health clinician, who will complete a
follow up assessment to obtain follow up outcome measures (MAS, SPPB, 2MWT, ESES SF-12) and
participants will be asked to complete the same survey again under the same conditions and
provisional support as the first survey (22-26). The results from the survey and the outcome
measures will be filed in the participant's rehabilitation centre file.

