3.5.1 Primary Outcome Measures

Feasibility of delivering the intervention will be in assessed using measures of adherence, acceptability, cost and safety. This will be collected by an allied health clinician at timepoints (T2), (T3) and (T4).

Adherence

Adherence will be measured by each participant in a workbook. The two measures of adherence will be percentage of sessions attended and number of repetitions completed per session will recorded in the participant's rehabilitation centre files. Attaining a personal best is encouraged in each session.

Acceptability

Acceptability will be determined via two methods, extracting perceived exertion (via the Borg Rating of Perceived Exertion (RPE scale)) from the practice sheets of participants at the study site at timepoints (T2), (T3) and (T4) and via purpose-built paper survey post intervention at timepoints (T3) and (T4) (28). The practice sheets will be stored on the participant's rehabilitation centre files. The paper survey will be provided in person by an allied health clinician from the study site. A paper survey was selected as in previous research at the study site there was a poor response to an electronic survey with participants requesting a paper-based survey. We expect the survey to take approximately 10 minutes to complete, participants will be given support to complete the study in clinic or may take the survey home to complete in time allocated outside the intervention. The

participant may receive support from a family member or carer. If requested, the allied health clinician may allocate time to assist in completion of the survey. Using a Likert scale, the survey will ask four questions:

- i) Were you satisfied with the program?
- ii) How easy was it to participate in the program?
- iii) Did the program give you adequate support?
- iv) Would you recommend the program?

They will also be given free text to input an answer to the following questions:

- i) What did you like or dislike about the multidisciplinary aspect of the program?
- ii) What did you like or dislike about the inclusion of Take Charge and participant workbook in the program?
- iii) What did you like or dislike about the amount of practice that was required?

Cost

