5.5 Proposed Sample Size

An approximate sample size of fifteen people will be recruited to participate in this study. This is likely to be reflective of the size of population recruited from the intervention run by the two sites.

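### Section 6.2 compares the T3 and T4 acceptability surveys only as frequencies, although the same people answer twice and their answers can be paired

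*Protocol*

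**What the plan says.** Acceptability is one of four components of the primary outcome, feasibility (Sections 3.2 and 3.5.1). It is measured in two ways: ratings of perceived exertion from the practice sheets, and a paper survey with four Likert items and three free-text questions.

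- **Repeat answers.** The survey is given at T3 and again at T4. Section 3.4 says that at T4 "participants will be asked to complete the same survey again under the same conditions and" support arrangements as for the first.
- **Analysis.** Section 6.2 says the survey data "will be reported as frequencies comparing time points week 3 (T3) and week 6 (T4). It mentions no pairing and no denominator. The same section specifies paired t-tests for the clinical outcomes.
- **Linkage.** Section 6.1 says data at each time point are extracted with "names replaced by individual participants study identification number".
- **Return of forms.** Under Section 3.5.1 the form is handed over in person and can be completed in clinic, or participants "may take the survey home to complete in time allocated outside the intervention". Section 3.4 adds that, if needed, a clinician or carer is available to "support filling out the survey and collecting the surveys from participant".
- **Size.** Section 5.5: "An approximate sample size of fifteen people will be recruited".

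**The concern.** The survey is a repeated measure on one small group, and Section 6.2 describes its change over time only through the frequencies at each occasion. Two things can go wrong.

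First, opposite moves cancel. If some people become less satisfied between T3 and T4 and the same number become more satisfied, the two frequency tables are identical and the change is invisible. This needs no missing data.

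Second, if a few people do not return the T4 form, the two tables describe different people. With about 15 participants one form is worth about 7 percentage points (1/15 = 6.7%), so a handful of missing forms can look like a change of opinion. T4 is the last study time point, so a form taken home then has no later study visit at which to hand it in. Section 5.7 deals with people who withdraw, but the protocol does not address people who stay in the study and do not return a form.

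At stake is how the T3 to T4 comparison is read for one part of the primary outcome. No test or success criterion is attached to it.

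**Working it through.** The protocol gives no survey response rate and no expected level of satisfaction, so there is no stated figure to reproduce. The only input from the document is n of about 15 (Section 5.5). The satisfied counts, the numbers of missing forms and the reduction of a Likert item to satisfied or not satisfied are assumptions for illustration.

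**1. What equal frequencies can hide.** Suppose 12 of 15 are satisfied at T3 and 12 of 15 at T4, with all forms returned. Let b people move from satisfied to not satisfied and c move the other way. Equal totals require b = c. Only 3 people were not satisfied at T3, so c is at most 3. The number of switchers, b + c, can therefore be anything from 0 to 2 × 3 = 6. A cross-table of T3 against T4 tells these cases apart; the two frequencies do not.

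**2. What missing T4 forms can create.** Suppose all 15 forms return at T3, s people are satisfied, nobody changes their answer, and k forms are missing at T4. The percentage satisfied among T4 returners lies between

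- lowest (satisfied people fail to return first): (s − k)/(15 − k)
- highest (dissatisfied people fail to return first): min(s, 15 − k)/(15 − k)

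With s = 12 (80.0% at T3):

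| Missing at T4 | Lowest | Highest |
|---|---|---|
| 0 | 12/15 = 80.0% | 12/15 = 80.0% |
| 1 | 11/14 = 78.6% | 12/14 = 85.7% |
| 2 | 10/13 = 76.9% | 12/13 = 92.3% |
| 3 | 9/12 = 75.0% | 12/12 = 100% |
| 5 | 7/10 = 70.0% | 10/10 = 100% |

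With s = 9 (60.0% at T3) and three missing, the range is 6/12 = 50.0% to 9/12 = 75.0%.

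**3. How likely the extremes are.** If forms go missing at random, the standard deviation of the spurious change for s = 12 is √[0.8 × 0.2/(15 − k) × k/14]. This gives 2.9, 4.2, 5.3 and 7.6 percentage points for k = 1, 2, 3 and 5. The chance that three forms missing at random are exactly the three from dissatisfied people is 1/455, about 0.2%. The ends of the ranges therefore need return to depend on satisfaction.

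**4. Effect of pairing.** Among people with both forms, nobody changing their answer gives a change of exactly 0 for every s and k above.

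**The case against.** The strongest objection is that Section 6.2 does not prescribe what is being criticised. It does not say that the two sets are unlinked, that percentages are taken over returners only, or that any test is applied. A reader might infer a deliberately unpaired analysis on returned forms, but the text is silent on both points, and a denominator rule could sit in an analysis plan not shown. The word used is frequencies. Read as counts, the extreme example gives 12 satisfied at both times, with the three missing forms visible in the totals.

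The protocol also guards against non-return. Home completion is only an option, the form is handed over in person, and help with completing and collecting it is available at both times. A reader might take the remark that "in previous research at the study site there was a poor response to an electronic survey" as evidence that forms will be lost. That response was to an electronic survey, and paper was chosen for that reason because participants asked for it. No return rate for paper forms is given.

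Most of this stands, and it limits the point about missing forms. It does not answer the point about individual change: counts or percentages, with every form returned, still cannot show who moved. On that point Section 6.2 does state a method, a comparison of frequencies, and a better one is available from the same data.

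**Conclusion.** The point holds as a modest improvement. For four Likert items answered twice by the same people under linked study numbers, a within-person comparison is more informative than comparing frequencies. Its value does not depend on missing data: equal frequencies of 12/15 are compatible with 0 to 6 people switching.

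The distortion from missing T4 forms is conditional. It is zero if all forms return. With three missing from an assumed 12/15 it runs from 75% to 100%, so it can go down as well as up. A reader might infer that non-return biases acceptability towards approval. That requires non-returners to be less satisfied, and nothing in the protocol supports or excludes it. A reader might also take the survey to be the main acceptability measure, but Section 3.5.1 lists it beside perceived exertion without ranking the two.

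The comparison is descriptive. The first research question in Section 2.4 asks whether the programme is acceptable, not whether opinion shifts, and no stated figure or threshold depends on the result.

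**What to change.** Add to Section 6.2, for each of the four Likert items:

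1. The T3 to T4 comparison is made within person, among those who answered both surveys, as a cross-table or as the numbers who moved up, stayed the same and moved down.
2. Beside the T3 and T4 frequencies, give the number of forms returned and not returned, out of the participants remaining in the data set at that time. Report withdrawals as a count only, because Section 5.7 keeps the results of people who withdraw out of the data set.

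A denominator of everyone who started the programme should not be used without first reconciling it with Section 5.7.

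The cost is one or two sentences of analysis wording and a slightly larger table. No new data, visits or participants are needed.

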2.4 Research questions

- 1.Is it feasible to deliver a multidisciplinary, short duration, intensive program for people after stroke using a self-management approach (in terms of adherence, acceptability, cost, and safety) in a community setting?
- 2. Does this approach warrant further investigation, indicated by an improvement of more than 10% in the main secondary measure of the study, mobility pre and post intervention?

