3.2 Study Design

The study will look at the feasibility of providing this type of training offered to clients attending the program at the study sites. As part of the intensive program, participants will undertake 45 hours (three hours for five consecutive days over three weeks) of intensive, multidisciplinary practice both in the clinic and at home. At-home therapy will be delivered by video-guided exercise programs or individualised exercise programs. The primary outcome measure for this study will be feasibility, measured by adherence, acceptability, cost and safety. The secondary outcome measures for this study will be mobility, quality of life, self-efficacy skills and goal attainment. Outcome measures will be collected just prior commencement (week 0) (T1), midpoint (second week) (T2), upon completion of the intensive program (third week) (T3) and three weeks post intensive program (T4).

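### Research question 2 turns on a mobility gain above 10%, but section 6.2 plans only tests against zero and mean differences, with no percentage change and no comparison with 10%

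*Protocol*

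**What the plan says.** Section 2.4 of the Protocol poses two research questions. The first is feasibility. The second begins "Does this approach warrant further investigation" and gives its own criterion: "indicated by an improvement of more than 10% in the main secondary measure of the study, mobility pre and post intervention". Sections 2.4 and 3.5.1 attach no numeric threshold to adherence, acceptability, cost or safety, so this 10% is the only numeric signal for going further.

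Section 6.2 fixes the analysis of all clinical outcomes together: "Paired t-tests will be used to analyse within group change over time for the clinical outcomes between week 0 (T1) to week 3 (T3", with the same comparison from T1 to T4. It adds: "Differences will be reported as a mean and 95% confidence interval". It gives no reference value for the tests other than the default of zero, no percentage change from T1, and no link to the 10% in section 2.4.

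Mobility is one of several secondary outcomes (section 3.2: "The secondary outcome measures for this study will be mobility, quality of life, self-efficacy skills and goal attainment"). Table 1 lists three measures under mobility: the MAS, the SPPB and the 2MWT. None is named as the one that carries the criterion.

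On size, section 5.5 says: "An approximate sample size of fifteen people will be recruited to participate in this study". The reason given is expected throughput: "This is likely to be reflective of the size of population recruited from the intervention run by the two sites". No effect size, SD or power is stated.

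**The concern.** The question asked and the analysis planned do not meet. The question is whether the gain exceeds 10%; the test asks whether the mean change differs from zero. A gain of 5% is a real change and can be statistically significant, yet it falls short of the study's own indicator. If 6.2 is followed as written, the report will contain p-values against zero and differences evidently in scale units. The reader then has to work out whether 10% was reached, on which scale, and with what uncertainty.

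What is at stake is the reading of research question 2. A significant p-value could be taken as a positive answer when the data do not support a gain above 10%, and with about 15 participants the uncertainty around any percentage gain is wide.

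**Working it through.** **Nothing to reproduce.** The sample size of 15 comes with no calculation. The check is therefore how the planned test behaves at gains that the 10% criterion does not count as enough.

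**Inputs**
- N = 15 (section 5.5), single group.
- Two-sided 5% level, taken as implied by the 95% interval in section 6.2.
- Threshold 10% (section 2.4).
- SD of individual change, as a percentage of the T1 mean: not in the protocol. Assumed range 10, 15, 20 and 30 points, with normally distributed changes.

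**Critical value and interval width.** t(0.975, 14) = 2.145. The 95% interval has half-width 2.145 × SD / √15 = 0.554 × SD. This is also the smallest observed mean gain that is significant against zero.

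**Probability of a significant gain.** For a true gain μ this is P(T′ > 2.145), where T′ is noncentral t with 14 df and noncentrality μ√15 / SD. For example, μ = 5 and SD = 10 give 5 × 3.873 / 10 = 1.94 and a probability of 0.438.

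| Assumed SD (points) | Half-width = smallest significant mean | Significant at true gain 5% | Significant at true gain 10% |
|---|---|---|---|
| 10 | 5.5 | 44% | 95% |
| 15 | 8.3 | 22% | 67% |
| 20 | 11.1 | 15% | 44% |
| 30 | 16.6 | 9% | 22% |

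**When the p-value and the observed gain disagree.** Setting 0.554 × SD = 10 gives SD = 10 × 3.873 / 2.145 = 18.1 points. If the SD in the sample is smaller than this, a result can be significant with an observed gain under 10%. If it is larger, any significant observed gain exceeds 10%. Because the sample SD varies around the true one, simulation shows how often the two disagree. At a true gain of 5%, the result is significant and the observed gain is 10% or less in about 41%, 13%, 3% and under 0.1% of studies for true SDs of 10, 15, 20 and 30.

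**Reading the criterion directly.** If question 2 is a rule on the observed mean, the chance of passing is P(mean > 10) = 1 − Φ((10 − μ)√15 / SD). At a true gain of 10% this is 50% for any SD. At a true gain of 5% it is 3%, 10%, 17% and 26% for SDs of 10, 15, 20 and 30. The answer to question 2 therefore depends on which quantity is set against which value, and 6.2 does not say.

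**The case against.** Several points on the other side stand.

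- **The interval is not tied to zero.** A reader might infer that both the planned test and the planned interval compare the change with zero. Only the test does. A confidence interval is an estimate that can be read against any value, including 10% of the T1 mean. What is missing is the scale and the link to the criterion.
- **The protocol does not frame 10% as a null hypothesis.** One might set the 95% to 22% rates at a true 10% gain against a nominal 2.5% and call them an inflated type I error. The documents do not support that. Section 2.4 is a research question that treats the gain as an indicator, which can be read as a rule on the observed mean, and the hypothesis in section 2.5 mentions neither 10% nor a mobility gain. The rates show what the zero-null test does at the threshold. They are not error rates of a test that the protocol claims to perform.
- **No section says that a significant t-test answers question 2.** The misreading is a risk left open, not an instruction. Testing change against zero is legitimate as a description of within-group change.
- **The rates depend on assumed SDs.** They vary widely over the range, and at the larger SDs a significant result with an observed gain under 10% is rare or nearly absent.

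It can also be argued that deriving a percentage is detail for a statistical analysis plan, which may exist. That argument does not dispose of the point. The protocol states both the question and the method, and the method as stated does not address the question, even if the criterion is a simple rule on the observed mean.

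**Conclusion.** The point holds as a gap between a stated criterion and a stated analysis. Section 6.2 contains no percentage change and no comparison with 10%, so the study's only numeric signal for further investigation has no analysis tied to it, and Table 1 leaves open which mobility measure it applies to. Significance against zero cannot fill the gap: a true gain of 5%, half the indicator, is significant in 44% of studies at an SD of 10 and in 9% at an SD of 30.

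These figures rest on 15 complete pairs, normal changes, a two-sided 5% level and SDs that are assumptions. The mismatch itself depends on none of them.

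A reader might also infer that the lower confidence limit ought to exceed 10%. The protocol sets no such bar. With 15 participants it would need an observed gain of 10 + 0.554 × SD, that is 15.5% to 26.6% over the SD range, so it should not be introduced as if already implied.

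Feasibility is the primary aim and mobility is secondary. The consequence is limited to how question 2 is answered. The change is worth making because it is nearly free.

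**What to change.** In section 6.2, add for research question 2:

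- the one mobility measure (MAS, SPPB or 2MWT) that carries the 10% criterion;
- that the T1 to T3 mean change will be reported as a percentage of the T1 mean, with its 95% confidence interval. The T1 mean is itself estimated, so the raw interval should not simply be divided by it. Analysing T3 − 1.10 × T1 with the same paired procedure shows where the interval lies relative to 10%;
- that question 2 is answered from this estimate against 10%, that the interval shows whether gains of 10% or less remain compatible with the data, and that the p-value against zero does not answer it.

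The paired t-tests against zero can stay as a description of within-group change in all outcomes.

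The cost is a few sentences and one derived variable, with no new data. The downside is that a modest gain will more often be described as a signal than as demonstrated.

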7.1 COVID impact

This project would ideally be implemented via in person therapy but can be adjusted to account for any social distancing or lockdown measures implemented because of COVID-19. In doing so the emphasis of the program may shift to more self-directed practice via remote methods, either via telehealth or via delivery of exercise programs using home-based programs and equipment or videos. If so, the program would emphasise the need for increased efficacy towards self-directed practice and could potentially identify any pragmatic determinants of implementing self-directed training. If this is the case, participants and relevant ethics committees will be notified before any changes are made to the investigation.

8 References

- (1) Eng, J. J., Chu, K. S., Kim, C. M., Dawson, A. S., Carswell, A., & Hepburn, K. E. (2003). A community-based group exercise program for persons with chronic stroke. *Medicine and Science in Sports and Exercise*, 35(8), 1271–1278. https://doi.org/10.1249/01.MSS.0000079079.58477.0B
- (5) Jones, T. M., Dean, C. M., Dear, B. F., Hush, J. M., & Titov, N. (2016). An Internet survey of the characteristics and physical activity of community-dwelling Australian adults with acquired brain injury: exploring interest in an internet-delivered self-management program focused on physical activity. Elsevier BV.
